This study proposes to conduct a 3-year pilot to explore the barriers and facilitators associated with EIMC acceptability, and the feasibility and acceptability of providing a novel EIMC strategy, “Like Father, Like Son” (LFLS) plus S&S, in CHCs in Lusaka, the Zambian capital. This pilot study would expand the impact of S&S by adopting a family-oriented approach to encourage pregnant couples to consider both EIMC for their neonates and VMMC for fathers and other uncircumcised males in the household. This study proposes to 1) match 8 clinics on past 12 month VMMC/EIMC rates and catchment size and randomize to intervention (n = 4 clinics, S&S+LFLS + VMMC/EIMC training) or observation conditions (n = 4 clinics, VMMC/EIMC training only), 2) utilize collaborative input from community stakeholders (n = 144; CHC Community Advisory Boards, patient focus groups, EIMC experts) at the 4 Experimental CHCs to develop study protocol, assessments, and LFLS intervention sessions, 2) establish formative, process and outcome evaluation criteria to assess feasibility and guide the implementation of the LFLS sessions, 3) enroll 300 pregnant couples (75 per experimental clinic over 18 months recruitment), 3) conduct baseline, pre- and immediately post-partum and 6-month post-partum assessments, and 4) evaluate acceptability and feasibility of S&S+LFLS at the CHC level, and the effect of S&S+LFLS on uptake of VMMC and EIMC. This study proposes to conduct a 3-year pilot study to explore the barriers and facilitators associated with early infant male circumcision (EIMC) acceptability, and the feasibility and acceptability of providing a novel EIMC strategy, “Like Father, Like Son” (LFLS) plus Spear & Shield (an evidence-based intervention), in community health centers (CHCs) in Lusaka, the Zambian capital. This pilot study would expand the impact of Spear & Shield by adopting a family-oriented approach to encourage pregnant couples to consider *both* early infant male circumcision (EIMC) for their neonates and voluntary medical male circumcision (VMMC) for fathers and other uncircumcised males in the household.

Aim 1. Develop, pilot and conduct formative, process and outcome evaluations to assess the CHC level feasibility and acceptability of S&S+LFLS.

Aim 2. Assess the intrapersonal, interpersonal, structural, and sociocultural factors relevant to the “Like Father, Like Son(s)” intervention, and develop program components to respond to these factors.

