Based on the IMB Model (information, motivation, behavioral skills) and the theory of planned behavior addressing normative behaviors (Ajzen & Fishbein, 1980) this exploratory study will examine the factors (e.g., father's circumcision and HIV status, paternal grandparents' and peer circumcision attitudes, mother's HIV status and circumcision attitudes) that underlie the decision to engage in VMMC and EIMC, and tailor the LFLS intervention component to respond to these factors. The study will offer S&S + LFLS to pregnant couples, targeting the perinatal period to address MC for both father and son(s), and pilot test the biobehavioral program, assessing feasibility of offering S&S+LFLS in Lusaka Province CHCs, the acceptability of the pilot program, and the potential of S&S+LFLS to optimize both VMMC and EIMC uptake.

Innovation

This application includes a number of innovative components. Promoting the bonding component of the father-son relationship, this application simultaneously addresses both the short and long-term HIV risk reduction goals associated with increasing availability and acceptability of male circumcision. We are unaware of any evidence-based effort in sub-Saharan Africa to stimulate prospective parents to simultaneously consider both EIMC and VMMC. The S&S + LFLS intervention could stimulate both EIMC and VMMC to occur during the pre- and immediate postnatal period, prior to resuming sexual activities, which corresponds with both mother and father undergoing healing following childbirth and VMMC, respectively. (N.B.: Our previous research found approximately 25% of the men undergoing VMMC were unable to abstain from sexual activities for the 6-week healing period; this group accounted for the majority of adverse events and dissatisfaction with VMMC). As most Zambian men are uncircumcised, a combined VMMC/EIMC program could encourage prospective fathers choosing to undergo VMMC to circumcise their male neonates, as well as other sons, procedures that would render their penises identical. Among men already circumcised, the program provides additional support for EIMC and VMMC for other sons. Finally, this program includes community health center EIMC sensitization, training and behavioral interventions, optimizing the impact of demand generation on uptake.

Impact

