Participants will meet with study staff and will be verbally screened for eligibility based on the following criteria, by study staff at each clinic.

CAB participants: CABs operate in each CHC clinic and are comprised of community zone leaders in the clinic catchment area; as zone leaders, they educate their community on the study objectives and sensitize their community on study goals, risks and benefits. Eligible CAB members will be men and women aged >18, representing a ward within each experimental CHC site catchment area. Twenty Community Advisory Board (CAB) member participants will be recruited from CABs at each clinic (20 CAB members x 4 clinics, n = 80), and each attendee will be compensated ~\$US10 per visit.

Focus Group participants. Stakeholder participants will be recruited from ANCs to attend gender specific focus group discussions (FGDs). A total of 8 pregnant couples from each of the 4 experimental CHC clinics (8 couples per clinic) will be recruited for this study [2 gender specific FGDs per clinic; (8 men and 8 women) x 4 clinics = 64 participants]. Both members of each couple must enroll to participate. Eligible participants will be pregnant couples (men and pregnant female partners) aged >18, attending the antenatal clinic of the experimental CHC. No personal, individually identifying information will be collected and no individual interviews or assessments will be conducted with FGD Members. Each attendee will be compensated ~\$US10 per visit.

IRB Study Number:

Version #, Date:

S&S+LFLS Participants. Pregnant couple participants (300 couples, n = 600 participants) will be recruited over 18 months via referral from ANC/VCT and enrolled as couples. A total of 75 pregnant couples will be recruited from each of the 4 clinics participating in LFLS (75 pregnant couples per clinic x 4 clinics = 300 couples = 600 individual men and women.) Both members of each couple must enroll to participate. Eligible women will be pregnant (up to 6 months pregnant), aged >18, any HIV status, and the partner of a male participant enrolling (neonates undergoing EIMC are receiving a clinical service approved by parents; only parents are study participants). Eligible men will be aged > 18, any HIV status [in accordance with Zambian and WHO/UNAIDS (2016) policy for MC eligibility], and the partner of the pregnant female participant enrolling. There is no upper age limit for participation, and each person will be compensated ~\$US10 per visit.

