Pregnant Couple Members attending LFLS. All S&S+LFLS study participants will be followed from enrollment to six months post-partum (maximum ~ time of participation based on enrollment at ~3-4 months pregnant = 12 months). Participants will complete baseline, pre-and post-partum and 6-months post-partum assessments and attend the Spear & Shield and 2 LFLS intervention sessions (see below).

Enrollment will be conducted from month 7 – 24, a total of 18 months.

11) **Study Endpoints***

Primary and secondary study endpoints.

Primary endpoints.

- EIMC uptake (infant)
- VMMC uptake (father and other sons)

Secondary endpoints.

- Father's and mother's circumcision attitudes

Primary or secondary safety endpoints.

This is a behavioral feasibility study, not requiring safety endpoints.

12) **Procedures Involved***

Design.

Like Father Like Son(s) proposes to develop intervention materials and test the effectiveness of the intervention to enhance the uptake of early infant male circumcision (EIMC) and voluntary medical male circumcision (VMMC) in the community health center (CHC) setting.

The study utilizes a longitudinal repeated measures design [2 (condition) x 4 (time points)]. The pilot study intervention will expand the Spear & Shield (S&S) intervention to include the “Like Father Like Son” component (S&S + LFLS).

IRB Study Number:

Version #, Date:

The pilot study will randomize 8 clinics to Experimental and Observation conditions; clinics will be matched on catchment area size and current EIMC and VMMC rates.

Experimental clinics (n = 4) will be trained to offer “S&S+LFLS”; Observation clinics (n = 4) will be “Observation Only” sites. Observation only sites will not recruit participants and will only be “observed” regarding the total number of VMMCs and EIMCs conducted at each individual clinic - Observation Only clinics will only provide clinic level aggregate data.

The study will train both Experimental and Observation Only clinic staff to conduct VMMC and EIMC procedures in order to provide equivalent services at all clinics, controlling for the availability of circumcision at all sites. Participants will only be recruited from experimental sites. The study will also assess the feasibility and acceptability of offering S&S+LFLS at the CHC level, and if successful, plan for a clinical trial of the S&S+LFLS intervention.

CAB Meetings & Focus Groups.

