1) Demographics, to include gender, age, marital status, male children MC status, education, income, father's MC status, HIV status (All public health facility users are required to undergo HIV testing per GRZ policy) (adapted, Kabwe, 2016 and [name] et al., 2015).

2) Stages of Change EIMC items (Precontemplation, Contemplation, Preparation, Action, Maintenance) will be adapted from Redding et al. (2015).

3) EIMC knowledge, norms, attitudes/beliefs items (adapted from [name] et al., 2010; Chilimampunga et al., 2017; Kabwe, 2015; Mugyawana et al., 2011; Waters et al., 2013; Young et al., 2016).

4) VMMC knowledge, norms, attitudes/beliefs items will be evaluated using an adaptation of Kebaabetswe et al. (2003), [name] et al. (2015)

5) EIMC/LFLS Intervention acceptability and feasibility at the clinic level will be assessed using an adaptation of Chilimampunga et al. (2017) and Mavhu et al. (2015). Topics include review of the

IRB Study Number:

Version #, Date:

S&S+LFLS model, and the incorporation of EIMC services in the clinic, advantages and/or disadvantages of the program, and changes or recommendations for the program. Staff and CAB members will participate in clinic meetings to evaluate feasibility and acceptability of the S&S+LFLS program.

- 6) EIMC decision making will be assessed using items adapted from the conceptual model developed by Mavhu et al. (2017).
- 7) EIMC/VMMC Individual level Uptake. EIMC outcome, male infant; VMMC outcome, fathers and sons in the household, sex of infant & birth status (M/F; Live/Lost). VMMC/EIMC uptake and the role of parents, family members, peers and HIV serostatus in the decision-making process will be assessed by telephone or private office visit at 6 months post-partum.
- 8) EIMC/VMMC Clinic level Uptake. CHCs will provide 12 months of historical VMMC/EIMC rate data prior to VMMC/EIMC and S&S+LFLS training. Clinics will also collect real-time comparative VMMC/EIMC monthly aggregate data for the duration of the study (Monthly EIMC/VMMC conducted following EIMC/VMMC training (M6) to M30). Historical period: Monthly CHC EIMC/VMMC conducted for 1 year prior to EIMC/VMMC training.

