Following baseline assessments, couples will complete a brief Stages of Change questionnaire prior to each prenatal and one-week post-partum LFLS sessions. Couples will be assessed at 6 months post-partum to evaluate EIMC and VMMC uptake by father, sons and infant to examine the interactive influence of EIMC and VMMC uptake, as well as the role of both parents, family members, peers and HIV serostatus in the decision-making process (Montaño et al., 2018; Mavhu et al. 2017; Cook et al., 2015; [name], Cook et al., 2014) (see Assessments).

13) Data and Specimen Banking* n/a

14) Data Management*

Analytic Plan and Power Analysis

Aim 1. Develop, pilot and conduct formative, process and outcome evaluations to assess the CHC level feasibility and acceptability of S&S+LFLS.

Aim 2. Assess the intrapersonal, interpersonal, structural, and sociocultural factors relevant to the LFLS intervention, and develop program components to respond to these factors.

Hypothesis 2. Father's circumcision status, paternal grandparents' circumcision attitudes, peer circumcision attitudes, father's HIV status, and mother's HIV status will be indirectly related to the decision to choose EIMC through the father's circumcision attitudes. A mother's circumcision attitudes will be influenced by her HIV status, and her protective attitudes toward the newborn which will also influence the father's circumcision attitudes.

Aim 3. Assess whether the combined S&S + LFLS pilot program will increase uptake of EIMC at clinic level.

Hypothesis 3. The S&S + LFLS experimental condition clinics will have significantly higher numbers of EIMC in comparison with observation condition clinics.

Hypothesis testing. The analyses for this feasibility pilot study will begin with examination of frequencies, means, skewness, and kurtosis across study variables (EIMC, VMMC, HIV status, attitudes) to assess normality. We will conduct 1) analysis of qualitative data, 2) a path model to explore undergirding sociocontextual factors of a father's decision to elect EIMC or VMMC for his male children, 3) a test of comparison between conditions.

IRB Study Number:

Version #, Date:

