H2. Assess factors relevant to the LFLS model. To investigate the indirect effects of the five main predictors (paternal grandparents' circumcision attitudes, peer attitudes surrounding circumcision, father's HIV status, father's circumcision status, and mother's HIV status) on infant circumcision, a path analysis (Kline, 2011) will be conducted. To estimate the indirect effects, it will be specified that the paths between the five main predictors on infant circumcision will act through father's circumcision attitudes. Mother's circumcision attitudes will be regressed on mother's HIV status, and a regression path between father's and mother's attitudes toward circumcision will be specified. When estimating the indirect effects, results will be adjusted for the effect of number of siblings circumcised.

All potential indirect effects will be estimated by a bootstrapping approach (MacKinnon et al., 2007). R-square of indirect effects will be used as measures of effect size (Fairchild et al., 2009). A sandwich estimator will be used to account for the nested data structure (e.g., individuals are nested by clinics). This estimator uses the Huber/White correction and adjusts for potential underestimated standard errors and bias in chi-square computation (Liang & Zeger 1986).

Missing data will be handled using Full Information Maximum Likelihood estimation procedures (Enders & Bandalos 2001). For model fit evaluations, we will use well-established fit indices and cutoff values: A well-fitting model ideally will have a non-significant model χ^2 , a Comparative Fit Index / Tucker-Lewis Index greater than .95, a root mean square error of approximation less than .08, and a standardized root mean square residual less than .08 (Hooper et al., 2008). All analyses will be conducted in Mplus (V8; Muthén & Muthén, 2017).

H3. Effect of S&S + LFLS pilot. To compare the proportion of EIMCs in the experimental group to the proportion found in the observation group, a one-sample z-test will be conducted. The population proportion will be taken to be the midpoint of the findings from Waters et al. (2013) on neonatal circumcision and historical numbers of circumcisions from Zambian clinics and hospitals. Based upon this rationale, the percentage of EIMCs in the observation group is anticipated to be approximately 5.0%.

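### VMMC uptake is a primary endpoint with a promised effect evaluation, but no between-condition VMMC analysis is planned and no at-risk denominator is defined

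*Combined protocol and SAP*

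**What the plan says.** **Endpoint and promise.** Section 11 gives two primary endpoints: EIMC uptake in the infant, and "VMMC uptake (father and other sons". No time point, denominator or summary measure is attached to the second. The Objectives say the study will evaluate "the effect of S&S+LFLS on uptake of VMMC and EIMC". The Design paragraph of section 12 says it will "test the effectiveness of the intervention to enhance the uptake of early infant male circumcision (EIMC) and voluntary medical male circumcision (VMMC".

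**Analysis.** In the Analytic Plan and Power Analysis (section 14), Aim 3 is limited to EIMC and Hypothesis 3 reads "The S&S + LFLS experimental condition clinics will have significantly higher numbers of EIMC in comparison with observation condition clinics". The H3 analysis is a one-sample z-test, introduced with "To compare the proportion of EIMCs in the experimental group to the proportion found in the observation group", against a reference of about 5.0%. The power statement concerns a 6-point difference in the EIMC rate.

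**Data.** Section 12, assessment item 8, says "Clinics will also collect real-time comparative VMMC/EIMC monthly aggregate data for the duration of the study", and also asks for 12 months of historical VMMC and EIMC counts. Observation clinics enrol nobody and supply clinic totals only. Assessment item 1 records the circumcision status of the father and of male children at baseline. Item 7 lists a VMMC outcome for fathers and sons.

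**Who is enrolled.** Section 7 states "Eligible men will be aged > 18, any HIV status" and sets no criterion on circumcision status. The Innovation part of section 6 expects circumcised men to take part: "Among men already circumcised, the program provides additional support for EIMC and VMMC for other sons".

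**The concern.** A primary endpoint normally leads to a stated contrast and a stated population. VMMC uptake has neither, yet the design is built to support a VMMC comparison: clinics are matched on VMMC rates, staff at all eight sites are trained in VMMC so that availability is equal, and VMMC totals are collected before and after training in both conditions.

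Two things are at stake. One of the two primary questions would go unanswered, or be answered by an analysis chosen after the counts are seen. Separately, the individual uptake figure from the experimental clinics would depend on an unstated choice: whether men who cannot have the event are counted in the denominator. The protocol intends to plan a later trial on these results, so both matter beyond the pilot.

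**Working it through.** **Step 1. Follow each primary endpoint through the plan.**

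| Element | EIMC | VMMC |
|---|---|---|
| Primary endpoint (section 11) | yes | yes |
| Effect promised (Objectives; section 12, Design) | yes | yes |
| Aim 3 and Hypothesis 3 | yes | no |
| Between-condition test (section 14, H3) | one-sample z-test | none |
| Reference rate | about 5.0% | none |
| Power | over 80% | none |
| Clinic counts, both conditions (section 12, item 8) | yes | yes |

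Two phrases in the hypothesis-testing overview of section 14 might seem to cover VMMC. The first is a comparison between conditions with no outcome named; the H3 paragraph then specifies it for EIMC alone. The second is a path model whose overview mentions VMMC for male children; the H2 paragraph then specifies infant circumcision as the outcome. That model also studies predictors of the decision, not the effect of condition.

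**Step 2. Reproduce the plan's only power figure.** Inputs from section 14: p0 = 0.05, p1 = 0.05 + 0.06 = 0.11, n = 140, two-sided 5%. For a one-sample test against a fixed rate:

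power = Φ[(p1 − p0 − 1.96·√(p0(1 − p0)/n)) / √(p1(1 − p1)/n)]

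= Φ[(0.06 − 1.96 × 0.01842) / 0.02644] = Φ(0.904) = 81.7%.

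This agrees with the stated value of over 80%. The figure belongs to EIMC. It cannot be carried over to VMMC, because no VMMC reference rate, effect or sample size is given.

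**Step 3. Effect of the denominator.** Let c be the share of enrolled fathers already circumcised. The documents do not give c, so I take a range from their population figures: 10.2% (traditional circumcision only, Lusaka; section 24), 22% nationally (section 6) and 23% nationally (Objectives). As an illustrative uptake among uncircumcised men I use the 40% reported for the experimental group of the earlier Spear & Shield trial (section 6).

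- Fathers at risk = 300 × (1 − c)
- Uptake over all fathers = 0.40 × (1 − c)
- 95% half-width for 40% among those at risk = 1.96·√(0.40 × 0.60 / at risk), ignoring clustering by clinic

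| c | At risk of 300 | 40% reads as | Half-width at 40% |
|---|---|---|---|
| 10.2% | 269 | 35.9% | 5.9 points |
| 22% | 234 | 31.2% | 6.3 points |
| 23% | 231 | 30.8% | 6.3 points |

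With all 300 fathers the half-width at 40% would be 5.5 points, so restricting the denominator costs less than one point of precision.

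**Step 4. What a clinic-level comparison can deliver.** The protocol says the eight clinics are matched and split four to four. I read this as four pairs, which it does not state outright. A within-pair permutation test has 2⁴ = 16 arrangements, so its smallest two-sided p-value is 2/16 = 0.125. Significance at 5% is out of reach for that test; an estimate with an interval is not.

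**The case against.** The strongest defence is that this is a feasibility pilot whose Aim 3 is openly limited to EIMC, so describing VMMC without testing it is reasonable. That stands as a design choice. It does not explain the primary label or the two statements that an effect on VMMC will be evaluated, and either the label and statements or the analysis has to change.

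A second defence concerns the denominator, and most of it stands. A reader might infer that the plan will produce a diluted uptake figure. The documents do not support that: nowhere are all 300 fathers set as the denominator, circumcision status is recorded at baseline, and the Objectives describe the target as fathers and other uncircumcised males in the household. The fault is that the denominator is undefined. Understatement follows only if all fathers are used.

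Three further inferences also go too far.

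- **That prior circumcisions will be counted as uptake.** This depends on the wording of the 6-month item, which is in an attachment not shown.
- **That fathers and sons will be pooled.** Section 11 puts them in one bullet, but the timeline and the 6-month assessment list them separately, and no composite is described.
- **That restricting to uncircumcised fathers would make the result comparable with the earlier trial's 40% versus 24%.** That trial enrolled HIV-negative men with no initial interest in VMMC. This one takes men of any HIV status in pregnant couples, and the protocol does not propose the comparison.

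It is also fair to object that clinic totals include every VMMC done at the clinic, so comparing them does not estimate uptake in enrolled families. This stands and shapes the fix.

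**Conclusion.** The point holds in two parts.

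First, VMMC uptake is a primary endpoint with a promised effect evaluation, and the plan as written yields no VMMC effect. This rests on the text alone. The gap is in the analysis, not in the data at clinic level. A reader might conclude that no VMMC comparison is possible; that is true only for individual-level uptake, since observation clinics enrol no participants.

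Second, the individual-level endpoint has no at-risk denominator although circumcised fathers are eligible. If all fathers were used, a true 40% would read as about 36% to 31%. That size assumes 10.2% to 23% of enrolled fathers are already circumcised. The lower figure covers traditional circumcision only and the upper ones are national, so the actual share could differ.

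**What to change.** 1. **Choose one course for the VMMC effect.**
   - Add a comparison of monthly clinic VMMC counts, four experimental against four observation clinics, respecting the matching and adjusting for the 12-month historical counts. Name it as a separate clinic-level endpoint, because the totals are not confined to enrolled families. Report an estimate with an interval and no significance claim, which also avoids adding a second primary test. Do not copy the one-sample z-test used for EIMC: it needs a fixed reference rate, which does not exist for VMMC, and it uses neither the observation-clinic counts nor the historical ones.
   - Or make VMMC a descriptive secondary endpoint, and reword the Objectives and the Design paragraph so that they no longer promise an effect.

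2. **Define individual uptake in the experimental clinics.** For fathers: a new circumcision between baseline and 6 months post-partum, among those uncircumcised at baseline. For other sons: the same definition, reported separately, among sons uncircumcised at baseline, so that families without such sons do not enter. The baseline circumcision-status items already planned are sufficient.

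The cost is protocol wording, at most one extra analysis of counts already being collected, and a denominator of about 231 to 269 fathers instead of 300 under the assumption above. No new data are needed.

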Exploratory analyses. To investigate change in EIMC attitudes, Stages of Change scores will be examined over time using an autoregressive modeling approach specifying the individual's stage at 1-week postpartum as the main outcome and individual's stage at baseline as a main predictor in the regression model (Hamaker et al., 2015). Variables from the previous path model will be included as potential covariates in attempting to explain stage movement. The estimated regression coefficient will reflect changes in EIMC attitudes over time. The model will use an ordinal logistic model to examine change over time. Odd ratios will be estimated as a measure of effect size (Chen et al., 2010).

Power. Using a two-tailed Z test to test the difference in proportions between two conditions at an α level of .05, this study has over 80% power to detect a difference of 6.0% in EIMC rate between the two conditions. This difference in proportion translates to an effect size of an odds ratio (OR) = 2.4, which is considered a small (OR = 1.68) to medium (OD = 3.47) effect size, according to Chen et al. (2010). This 2.4 OR is based on an effect size found in previous research examining circumcisions ([name] et al., 2015). With these specified parameters, 80% power is achieved with 140 couples (out of ~151 couples with male infants).

Data Security. CAB and FGD participants will not provide any uniquely identifying information during participation in group discussion sessions. Pregnant couple participants in the intervention will be assigned a unique code upon entering the study. This number will identify all participant files, which will include no identifiable information. Access to the computer data files will be restricted by password codes. The list translating participant number to identifying information

IRB Study Number:

Version #, Date:

will be maintained in a secure locked file in the Spear & Shield study office in Lusaka at the University of Zambia School of Medicine. Participants will be made explicitly aware at the time of the informed consent of the nature of the separate record that will be kept for them. CAB and focus group discussions will be audio-taped for review and summary of key discussion points; copies will be stored in a locked cabinet at the PI's Lusaka offices, and deleted following summarization.

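### Hypothesis 3 is tested as a proportion, but no birth denominator is specified for the observation clinics, so an assumed 5% replaces the randomised control arm

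*Combined protocol and SAP*

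**What the plan says.** Section 14 (Data Management) words Hypothesis 3 as a count: "experimental condition clinics will have significantly higher numbers of EIMC in comparison with observation condition clinics". The H3 analysis paragraph of the same section changes the measure; its purpose is "To compare the proportion of EIMCs in the experimental group to the proportion found in the observation group". The method is that "a one-sample z-test will be conducted", with a reference value taken midway between a published Zambian study and historical circumcision numbers: "the percentage of EIMCs in the observation group is anticipated to be approximately 5.0". The power paragraph describes something else again: "Using a two-tailed Z test to test the difference in proportions between two conditions at an α level of .05".

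On data, Section 12 (Design) says that observation sites enrol no participants, supply clinic-level aggregates only, and are observed "regarding the total number of VMMCs and EIMCs conducted at each individual clinic". Item 8 of the assessments in Section 12 (Clinic level Uptake) defines the study-period data as "Monthly EIMC/VMMC conducted following EIMC/VMMC training (M6) to M30". It calls the 12-month historical data rate data, but then defines them too as monthly procedures conducted.

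Births enter elsewhere in two ways. More than 150 births per month is a site-selection criterion (Sections 9 and 24). Infant sex and birth status are recorded under individual-level uptake (Section 12, item 7), which covers enrolled couples, and these come from experimental clinics only.

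**The concern.** A proportion needs a denominator. In the experimental clinics, enrolled couples with male infants provide one. In the observation clinics, the listed data are procedure totals, and nothing says that male births will be counted beside them. The two-arm comparison that H3 announces therefore has only one measured side, and a fixed 5% supplies the other.

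EIMC uptake is a primary endpoint (Section 11), and Aim 3 asks about uptake at clinic level. If the true control rate lies well below 5%, a large relative gain could be missed. If training and supplies alone lift it above 5%, a gain could be credited to the intervention wrongly. Counts from the observation clinics could be set beside the experimental counts, but they also reflect how many boys were born at each clinic, and no analysis is planned that allows for this.

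**Working it through.** **1. The plan's own sample size.** Inputs from Section 14: p0 = 0.05, OR = 2.4, two-sided α = 0.05, power 80%, 140 couples with male infants.

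- p1 = 2.4 × (0.05/0.95) / [1 + 2.4 × (0.05/0.95)] = 0.1263/1.1263 = 0.1121.
- One-sample z-test: n = [(1.960√(p0q0) + 0.842√(p1q1)) / (p1 − p0)]² = [(0.4272 + 0.2656)/0.0621]² = 124.2.
- With continuity correction: n/4 × [1 + √(1 + 2/(n(p1 − p0)))]² = 139.9, so **140**. The stated figure is reproduced.
- A two-sample z-test with the same inputs needs 302 per arm (334 with correction). For 5% against 11% it needs 320 per arm, and 140 per arm gives 45.6% power.

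So 140 fits a calculation that treats 5% as a known constant, not one that estimates a rate in the observation clinics.

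**2. What the listed data identify.** Assumptions: half of births are male; the M6 to M30 window is 24 months. Suppose that the four observation clinics report 360 EIMCs. The implied proportion is 360 / (4 × births per month × 0.5 × 24):

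| Births per clinic per month | Male births, 4 clinics | Implied proportion |
|---|---|---|
| 150 (the site threshold) | 7,200 | 5.0% |
| 200 | 9,600 | 3.75% |
| 300 | 14,400 | 2.5% |
| 600 | 28,800 | 1.25% |

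The site criterion sets a floor and no ceiling, so the counts alone do not determine the proportion.

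**3. How safe 5% is as a stand-in.** Section 6 reports about 0.02% of male infants in EIMC-trained Lusaka clinics in 2018 and 1,181/362,078 = 0.33% nationally. It also cites 11% in the published study behind the midpoint. As an illustration, a control rate of 0.33% and an experimental rate of 3% would be a nine-fold rise (3/0.33 = 9.1) that still falls below the 5% reference.

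**4. Births and raw counts.** Assume 75 male births per clinic per month (half of 150), four clinics per arm, 24 months and a 5% rate in both arms. The expected count is 0.05 × 7,200 = 360 per arm. With more births in one arm and no effect, and z = (difference)/√(sum of the counts):

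| Ratio of births | EIMC counts | Naive Poisson p |
|---|---|---|
| 1.0 | 360 v 360 | 1.0 |
| 1.1 | 396 v 360 | 0.19 |
| 1.25 | 450 v 360 | 0.002 |
| 1.5 | 540 v 360 | <0.0001 |

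**5. The planned effect on the clinic scale.** Six points among about 151 enrolled male infants is 151 × 0.06 = 9.06 extra EIMCs. If nobody outside the enrolled couples is affected, that is 9.06/7,200 = 0.13 points, or 5.00% to 5.13%. A births imbalance of 9.06/360 = 2.5% would give the same gap in counts.

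**The case against.** Five points on the other side deserve weight.

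- *Size is controlled by design.* Sections 12 and 24 match clinics on catchment size and on EIMC and VMMC rates before randomisation. A reader might infer that raw counts are confounded by clinic size, since the candidate sites are labelled large, medium and small. The documents do not support that. If matching balances births there is no distortion, as the first row of the table in step 4 shows. What stands is that catchment size is not births, there are only four clinics per arm, and the analysis has no adjustment for what remains.
- *The planned test can run.* It needs only the enrolled couples and the 5%. That is correct, and it is why the observation clinics drop out of it.
- *Aim 3 is not beyond reach.* A reader might infer that the trial's own data cannot answer it. That goes too far: monthly counts with a 12-month baseline at all eight clinics could support an analysis of within-clinic change, which removes stable size differences. No such analysis is specified.
- *The gap may not be permanent.* Every site has a maternity ward, and Section 6 already quotes a per-male-infant figure from clinic data, so birth counts may be retrievable later. The plan does not provide for this.
- *The forms are not on view.* Section 12 says that the data collection forms are still being developed. The supportable statement is that a birth count is not specified, not that it will be absent. Speaking of rates hints at a denominator, but item 8 defines the data as procedures conducted.

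**Conclusion.** The point stands in this form. The hypothesis (numbers), the test (a proportion against a constant) and the observation-clinic data (procedure totals) do not fit together. From the data listed, no observation-arm proportion can be computed, and the randomised observation clinics play no part in the H3 test. The 5% used instead is about 15 times the national figure in Section 6 (5/0.33) and 250 times the trained-clinic figure (5/0.02), although it is below the 11% in the cited study. Rates after training at the study sites are unknown, so the direction of any error is open.

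The size of the births problem rests on assumptions: 75 male births per clinic per month, 24 months, an equal 5% rate, and Poisson counts that ignore clustering. On these, 25% more births in one arm gives 450 against 360 EIMCs with no effect. This shows what an unadjusted comparison of counts would be exposed to; the documents give no evidence that such an imbalance exists.

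**What to change.** 1. Add male live births per month to the aggregate data from all eight clinics, for the 12 historical months and every study month, retrieved from maternity records where needed.
2. Define clinic-level uptake as EIMCs per male live birth, and reword Hypothesis 3 in the Objectives and in Section 14 to match.
3. Replace the one-sample test against 5% with a comparison of arms at clinic level on that measure. It should use the historical rate as baseline and respect the matching and the eight clusters; a rate model with log male births as offset is one option. Enrolled-couple uptake should be reported separately, because consenting couples and all clinic births are different populations.
4. Restate the power.

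The data cost is one extra form field and some retrieval work. The larger cost is that the stated 80% does not carry over. With the dilution in step 5 and clustering ignored, the standard error of the difference is about √(2 × 0.05 × 0.95/7,200) = 0.0036. The expected z is then 0.00126/0.0036 = 0.35, and power is about 6%. A detectable result would need an effect well beyond the enrolled couples. For a feasibility pilot, the clinic-level result may be better presented as an estimate with its interval.
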